Patients will be randomised using the simple randomisation service provided by Sealed Envelope Ltd. This is an online service that provides random permuted block randomisation, ensuring participants are balanced between the control and treatment group. The physician will use a unique URL and password to randomise patients in A (treatment) or B (control) group.

Patients will receive injections containing one of the two following solutions, delivered under landmarks guidance to treat either; trigger finger, de Quervains tenosynovitis or carpal tunnel. Both combinations are used as part of routine practice for soft tissue corticosteroid injections in the hand and wrist at University Hospital NHS Trust by the local Hand and Wrist surgeons:

- A. 1ml of triamcinolone (40mg/1ml)
- or
- B. 1ml of triamcinolone (40mg/1ml) + 1ml 1% Lidocaine

The registrar will draw up, prepare the treatment in a separate room so that the patient will remain blinded. Neither treatment can be distinguished from one another by their appearance alone.

During the clinic appointment the patient will complete a pain VAS score prior to the injection, for pain experience at the time of the injection and at 5 minutes post injection on the patient assessment record. The pain VAS score of the pain experience during the corticosteroid steroid will be recorded immediately after the procedure. The patient then takes the patient assessment record home to complete further pain VAS scores at; 1-hour, 2-hour, 3-hour and 24-hours following the injection. The timings at which these scores must be recorded will be clearly documented on the patient assessment record by the physician before leaving clinic to help remind the patient. There are three further questions, on the same form; that the patient will be required to answer at 3-hours post injection (Appendix 4).

During the first 3-hours after your steroid injection:

1. Did you take any additional painkillers because of pain at the injection site?

YES Medication: _____

Time taken: _____

NO (go to next question)

2. Did you have any reduction in hand function, below normal, as a result of the injection?

YES please describe your reduction in function:

NO

3. Did you experience any new numbness in your hand, as a result of the injection?

YES

NO

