After the final pain VAS score at 24-hours the patient will receive a follow-up call by the registrar to ensure the assessment form has been completed, to answer any questions and remind the patient to

[figure not shown]
return the form using the prepaid envelope provided. After the form is posted the patients participation in the study will be complete.

The routine dictated clinic letter completed by the physician will outline the patients diagnosis, inclusion into the trial, and an overview of the trial and the consent process, but will not specify which treatment was delivered. A copy of this letter is kept in the patients' notes and a copy is sent to the GP.

The patient participation record and a copy of the consent form will be kept in the site file and stored in a locked filling cabinet in [name], Level 11, Derriford Hospital.

Returned patient assessment records will be collected by the departmental secretary, held within the site file and remain sealed until the end of recruitment. Once the recruitment phase is completed the patient assessment records will be open and the pain VAS scores will be measured, recorded on an excel spread sheet then statistically analysed by a blinded assessor ([name] - A member of the study management team, but directly not involved in patient recruitment). The same individual, who will not be involved in patient recruitment, will take all the measurements. Measurements will be taken using a standard 20cm ruler with 1mm increments and recorded to the nearest. Incomplete patient assessment records will be included on an intention to treat basis. A summary of the investigations, treatment and assessment can be found in Appendix 5. A planned time for the SToICAL study is outline in a Chart (Appendix 6)

Patient recruitment process during outpatient clinic:

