5.2 REPORTING PROCEDURES

All adverse events should be reported. Depending on the nature of the event the reporting procedures below should be followed. Any questions concerning adverse event reporting should be directed to the Chief Investigator in the first instance.

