5.3 RESPONSIBILITIES

5.3.1 Principal Investigator (PI):

Checking for AEs and ARs when participants attend for treatment / follow-up.

1. Using medical judgement in assigning seriousness, causality and expectedness using the Reference Safety Information approved for the trial.
2. Using medical judgement in assigning seriousness and causality and providing an opinion on expectedness using the Reference Safety Information approved for the trial.
3. Ensuring that all SAEs and SARs (including SUSARs) are recorded and reported to the Sponsor within 24 hours of becoming aware of the event and provide further follow-up information as soon

as available. Ensuring that SAEs and SARs (including SUSARs) are chased with Sponsor if a record of receipt is not received within 2 working days of initial reporting.

4. Ensuring that AEs and ARs are recorded and reported to the Sponsor in line with the requirements of the protocol.

5.3.2 Chief Investigator (CI) or delegate:

1. Clinical oversight of the safety of patients participating in the trial, including an ongoing review of the risk / benefit.
2. Using medical judgement in assigning seriousness, causality and expectedness of SAEs where it has not been possible to obtain local medical assessment.
3. Using medical judgement in assigning expectedness.
4. Immediate review of all SUSARs.
5. Review of specific SAEs and SARs in accordance with the trial risk assessment and protocol as detailed in the Trial Monitoring Plan.

5.3.3 Sponsor:

1. Acknowledgement of reported SAEs, SARs and SUSARs according to the trial protocol.
2. Expedited reporting of SUSARs and Urgent Safety Measures to the Competent Authority (MHRA in UK) and REC within required timelines.
3. The unblinding of a participant for the purpose of expedited SUSAR reporting.
4. Checking for (annually) and notifying PIs of updates to the Reference Safety Information for the trial.
5. Preparing standard tables and other relevant information for annual reports in collaboration with the CI and ensuring timely submission to the MHRA and REC.

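### Adverse events after the patient leaves clinic are left to spontaneous report during recruitment: forms stay sealed and the 24-hour call includes no adverse event question

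*Combined protocol and SAP*

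**What the plan says.** **After the injection (section 3, Study design).** The patient completes a score in clinic at 5 minutes and takes the form home. It holds the later VAS scores and three questions about the first 3 hours: extra painkillers, reduced hand function, and numbness ("Did you experience any new numbness in your hand, as a result of the injection").

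**The call.** After the 24-hour score there is "a follow-up call by the registrar to ensure the assessment form has been completed, to answer any questions and remind the patient to" post it. Participation ends when the form is posted.

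**The forms.** They are collected by the departmental secretary, "held within the site file and remain sealed until the end of recruitment". What follows is described as measurement and analysis: "Once the recruitment phase is completed the patient assessment records will be open and the pain VAS scores will be measured". Section 7.1 reports the answers on analgesia and function as numbers, without statistical testing. No section sends a positive answer to an adverse event record.

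**The safety duties (section 5).** Section 5.2 states: "All adverse events should be reported". Section 5.2.1 extends recording to every non-serious event, expected or not. Section 5.3.1 gives the PI the task of "Checking for AEs and ARs when participants attend for treatment / follow-up". Section 5.3.2 gives the CI "Clinical oversight of the safety of patients participating in the trial, including an ongoing review of the risk / benefit".

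**The concern.** Section 5 sets a standard of complete adverse event recording and continuing review. Section 3 describes no step after the patient leaves that would supply the information while the trial is recruiting. The one item collected from every patient who returns a form is closed until recruitment ends. The one conversation planned with every patient has no adverse event enquiry among its purposes.

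Two things are at stake. First, a problem that persists after clinic reaches the investigators only if the patient raises it, so the CI's review may have little to work on. Second, event counts would reflect which patients chose to speak up. A comparison of adverse events between arms, or a statement that either injection was free of them, would then have weak support.

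**Working it through.** **1. How long the forms stay sealed**

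Inputs:
- 3.6 injections per week and 60% capture (section 3.1)
- a target of 100 patients (sections 3.1 and 4.1)
- the anecdotal range of 3 to 5 injections per week (section 1.1)

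The plan's own figure comes first. Recruitment rate = 3.6 × 0.60 = 2.16 patients per week. Over 52 weeks, 2.16 × 52 = 112 patients, so the plan's statement that 100 can be reached within 12 months is reproduced.

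- Time to 100 patients = 100 / 2.16 = 46.3 weeks. This is roughly how long the earliest returned forms stay sealed.
- Average sealing time = 46.3 / 2 = 23.1 weeks, assuming even accrual and prompt return.
- At 3 injections per week: 100 / (3 × 0.60) = 55.6 weeks.
- At 5 injections per week: 100 / (5 × 0.60) = 33.3 weeks.

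**2. Which routes could carry an adverse event to the investigators during recruitment**

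| Route | Where | What it provides |
|---|---|---|
| In clinic, to 5 minutes after injection | Sections 3, 5.3.1 | An adverse event check at treatment is assigned, but covers only the first minutes |
| 24-hour call | Section 3 | Form completion, questions, reminder to post; no adverse event enquiry stated |
| Follow-up attendance | Section 5.3.1 | Check assigned, but no such attendance is scheduled |
| Posted form | Section 3 | Sealed until recruitment ends |
| Registrar's contact details | Section 4.1 | Given for further study information; depends on the patient making contact |
| Monthly management meeting | Section 10 | Potential issues are discussed; adverse event data are not named as an input |

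Once the patient has left clinic, each route that is open during recruitment depends on the patient volunteering the information.

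**3. What the sealed questions could show**

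The function and numbness questions cover the first 3 hours. Section 1.1 gives lidocaine's effect as 1 to 3 hours, and section 1.2 expects it may cause paraesthesia and hinder normal use of the hand while it acts. A temporary block and the start of lasting numbness would both be answered yes. Section 1.1 also says a post-injection flare can last 2 to 3 days. No question asks whether anything is still present at 24 hours. The missing element is therefore an enquiry about persistence, which opening the forms early would not supply.

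**The case against.** **The duties can still be discharged.** A reader might infer that section 3 makes sections 5.2 and 5.3.2 impossible to meet, or that a site following it is in breach. The documents do not support that. The serious event clock in section 5.2.2 runs from staff becoming aware, so a sealed form delays awareness without breaking the rule. Setting 46 weeks of sealing against that 24-hour limit compares two different clocks. Section 5.2.1 sets no deadline for non-serious events, so they could be recorded at unsealing. This objection stands: the duties are not assured, which is less than unachievable.

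**Other routes exist.** A clinician speaks to each patient partly to answer questions, the patient holds contact details, the GP is told of trial inclusion, and follow-up in section 5.3.1 could be read to cover the call. All of this is fair. But section 3 does not carry the check into the call, and the other routes rely on the patient or GP speaking first.

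**The harm may be rare.** It is tempting to apply the 15–20% transient rate in section 1.1 to all 100 patients and expect 15 to 20 missed events. That rate is for carpal tunnel injections and covers pain, bruising and flushing; pain is already scored on the VAS. The same section reports no adverse events in the trigger finger and de Quervains reviews, and severe effects below 0.1% after carpal tunnel injection. No count of missed events can be drawn from the documents.

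**Sealing has a purpose.** It keeps the VAS records closed until the blinded assessor measures them, and the 3-hour questions are outcome items, not a safety screen. Reading them early would be a weak remedy. This also stands.

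**Some material is not in the text.** The appendices and the Trial Monitoring Plan are not available here, and a figure interrupts the description of the call. An adverse event prompt could appear in one of them.

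**Conclusion.** The point holds as an inconsistency between section 3 and sections 5.2, 5.2.1, 5.3.1 and 5.3.2. As written, adverse event capture after clinic rests on spontaneous report throughout recruitment. Complete recording and ongoing risk/benefit review are not assured, and adverse event frequencies by arm would be unreliable.

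The only size that can be given is the sealing time: about 46 weeks for the earliest forms and 23 weeks on average, with full recruitment taking 33 to 56 weeks at 5 to 3 injections per week. This assumes 60% capture, even accrual and prompt return. The point also assumes that no adverse event prompt sits in material absent from the text.

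This should be fixed before enrolment. The primary analysis, change in VAS from baseline to 1 hour, is not affected.

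**What to change.** Reconcile section 3 with sections 5.2, 5.2.1, 5.3.1 and 5.3.2 by building the check into the existing call:

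- Add a fixed-wording, open adverse event question, including whether any new numbness or reduced function is still present.
- Ask it only after the patient confirms that the 24-hour VAS and the three form questions are already completed.
- Record the answers on an adverse event log kept apart from the sealed form, and pass them to the PI for assessment under section 5.
- Reword section 5.3.1 so that follow-up names the call.
- Make the log a stated input to the CI's review and to the monthly meeting in section 10.
- Keep the forms sealed as now.

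The cost is a few lines of protocol text, a short script and a log page, on a call already planned for every patient. There are two small downsides. The registrar randomises the patient and prepares the injection, so the caller knows the allocation; this is why the wording must be fixed. The patient may also still hold the unposted form, so asking last reduces the risk of altered answers but does not remove it.

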3.1 STUDY OUTCOME MEASURES

Patients pain will be measured using a 100mm pain VAS score which they will complete on a paper form; before the injection, at the time of injection, then 5-minutes, 1-hour, 2-hours, 3-hours and 24-hours after the injection. Patients will remain active in the study until the final VAS score is completed and the form is returned.

Assessment of additional analgesia required and any reduction in hand function will be determined by the patients answers to the following three question, which are completed 3-hours after the injection (Appendix 5).

During the first 3-hours after your steroid injection:

1. Did you take any additional painkillers because of pain at the injection site?

YES Medication: _____

Time taken: _____

NO (go to next question)

2. Did you have any reduction in hand function, below normal, as a result of the injection?

YES please describe your reduction in function:

NO

3. Did you experience any new numbness in your hand, as a result of the injection?

YES

NO

The study will end once 100 patients have been recruited, which includes 82 patients to achieve 95% power, plus 20% to account for potential dropouts. With an average of 3.6 corticosteroid injections given every week and an estimated 60% capture rate, full recruitment should be achievable within 12 months.

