1.2 RATIONALE FOR CURRENT STUDY

Study: The SToICAL Study

The authors are not aware that a study exists that assesses pain following soft tissue corticosteroid injections in the hand and wrist, co-administered with and without local anaesthetic. Although, corticosteroids and local anaesthetic are often co-administered no evidence is currently available to support this.

The effects of the local anaesthetic only last for 2-3 hours; therefore it would not provide relief from post-procedure flares nor bridge the time until the corticosteroid becomes effective. Administering local anaesthetic can be painful because of the acidity of the solution and means higher volume injections are given. The use of local anaesthetic may also worsen paraesthesia symptoms or result in paraesthesia in parts of the hand, preventing normal function for the duration of its action.

Adding local anaesthetic increases the cost, time and clinical waste of the treatment. Although, the additional cost per treatment may not be significant when considering the number performed across the National Health Service, the saving may be considerable.

We hypothesise, that the pain experienced at 1-hour after a corticosteroid injection for trigger finger, de Quervains tenosynovitis and carpal tunnel syndrome is no worse than when the corticosteroid is co-administered with local anaesthetic.

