2. STUDY OBJECTIVES

The primary objective:

Investigate whether there is a difference in pain VAS scores at 1-hour after a corticosteroid injection for trigger finger, de Quervains tenosynovitis or carpal tunnel syndrome co-administered with or without local anaesthetic.

The secondary objectives:

i) Investigate whether there is a difference in pain VAS scores during the 24-hours after a corticosteroid injection for trigger finger, de Quervains tenosynovitis or carpal tunnel syndrome co-administered with or without local anaesthetic.

ii) Investigate whether there is a difference in the pain VAS scores at the time of the corticosteroid injection for trigger finger, de Quervains tenosynovitis or carpal tunnel syndrome co-administered with or without local anaesthetic.

[figure not shown]
iii) Investigate the difference in the additional analgesia required and in the functional use of the hand during the first 3 hours following a corticosteroid injection for trigger finger, de Quervains tenosynovitis or carpal tunnel syndrome co-administered with or without local anaesthetic.

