4.3 INCLUSION CRITERIA

- Male or female ages $>/= 18$ years
- A clinical diagnosis of trigger finger, de Quervains tenosynovitis or carpal tunnel syndrome made by a consultant physician.
 - Trigger finger: A diagnosis made on a history of triggering together with clinical findings of pain localised to the first annular pulley along with triggering of the affected digit
 - De Quervains tenosynovitis: A diagnosis made on clinical examination findings of pain over the first dorsal compartment, swelling localised to the first dorsal compartment and a positive Finklestein test.
 - Carpal tunnel syndrome: A diagnosis made on a history of intermittent paraesthesia in the radial 3.5 digits, with nocturnal symptoms and subjective sensory impairment and thumb weakness.
- Treatment with corticosteroid injection is recommended by the doctor and agreed by the patient
- Patient is willing and able to give informed consent for participation in the study

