Outcome measure: The percentage of patients requiring additional analgesia or who experienced worsening hand function will be determined from the three questions asked in the patient assessment record. The results will be presented as numbers with additional details given in the patients' response, but no statistical analysis will be performed on these results.

No interim or subgroup analysis will be performed.

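### The numbness question does not ask about worsening of existing numbness, and the function question has no stated reference point, so these descriptive results may under-count and are hard to interpret in patients impaired at entry

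*Combined protocol and SAP*

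**What the plan says.** Secondary objective iii (section 2) is to "Investigate the difference in the additional analgesia required and in the functional use of the hand during the first 3 hours". Sections 3 and 3.1 give the three questions that serve it, all answered 3 hours after injection:

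- Analgesia: "Did you take any additional painkillers because of pain at the injection site", with the drug and time recorded.
- Function: "Did you have any reduction in hand function, below normal, as a result of the injection", with the prompt "YES please describe your reduction in function".
- Numbness: "Did you experience any new numbness in your hand, as a result of the injection", yes or no only.

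Section 7.1 (objective iii) then says that the percentage needing analgesia or "who experienced worsening hand function will be determined from the three questions". These results are to be shown as numbers with the patients' own descriptions and are not tested.

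Two other places matter. Section 1.2 argues against adding local anaesthetic partly because "The use of local anaesthetic may also worsen paraesthesia symptoms or result in paraesthesia in parts of the hand". Section 4.3 defines carpal tunnel syndrome for entry as "A diagnosis made on a history of intermittent paraesthesia in the radial 3.5 digits", together with subjective sensory impairment and thumb weakness.

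**The concern.** Numbness and loss of function are among the protocol's own reasons for wanting to leave out the local anaesthetic. Section 1.2 names two sensory effects: existing paraesthesia gets worse, or paraesthesia appears. The numbness question covers only the second. A carpal tunnel patient whose existing numbness deepens can properly answer no, and without free text that answer cannot be reinterpreted later.

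The function question has a different weakness. Many participants arrive with a hand that is already not normal, and the question does not say what normal means. One patient may compare with a healthy hand and another with the hand as it was that morning. Section 7.1 nevertheless labels the result as worsening.

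At stake is what the reported counts mean. An effect that the protocol attributes to local anaesthetic could be under-counted, mainly in the arm that receives it.

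**Working it through.** The point turns on wording, so the main check sets the sections side by side.

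**Numbness**

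| Effect named in section 1.2 | Who can have it | Asked about at 3 hours? |
|---|---|---|
| Paraesthesia arising in parts of the hand | Any participant | Yes, as new numbness |
| Worsening of existing paraesthesia | Patients with paraesthesia at entry; by section 4.3 this is an entry feature of carpal tunnel syndrome only | No |

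**Function**

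- Section 4.3 requires triggering for trigger finger and thumb weakness for carpal tunnel syndrome. Section 1.1 also lists dysfunction for trigger finger. Impairment at entry is therefore expected in at least two of the three diagnoses.
- The only patient-reported measure before injection described in sections 3 and 3.1 is the pain VAS, so a change in function or numbness cannot be derived.
- Section 7.1 needs a change, because it reports worsening.

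**Could the gap be closed later?** Nothing described does so. Returned forms stay sealed until recruitment ends (section 3). The call after 24 hours is for checking completion, answering questions and prompting return. No subgroup analysis is planned (section 7.1), so dependence on diagnosis would not show.

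**The plan's figure.** The sample size concerns the 1-hour VAS and is not touched by this point. It reproduces with margin 20 mm, SD 25 mm, power 95% (section 7.2) and two-sided 5% (section 7.3):

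n per arm = 2 × (1.960 + 1.645)² × 25² / 20² = 2 × 12.995 × 1.5625 = 40.6, rounded up to 41, or 82 in total.

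**Illustration of size (every input here is an assumption).** Let c be the carpal tunnel share, p the true rate of new or worse numbness, taken as equal in every diagnosis, and m the fraction of it that the question misses in carpal tunnel patients. Then observed rate = p × (1 − c × m). With p = 30% and 41 patients per arm:

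| c | Carpal tunnel patients per arm (41 × c) | Observed rate, m = 0.5 | Observed rate, m = 1 |
|---|---|---|---|
| 10% | 4.1 | 28.5% | 27% |
| 30% | 12.3 | 25.5% | 21% |
| 50% | 20.5 | 22.5% | 15% |

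If c and m are the same in both arms, the absolute difference between arms shrinks by the same factor, 1 − c × m. At m = 1 that is 0.90, 0.70 or 0.50. The documents do not say which row applies.

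**The case against.** The strongest reply is that little is lost.

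- **Function.** The question asks about a reduction attributed to the injection and invites a description. A patient with long-standing triggering is not asked to report it, and worsened numbness that impairs use of the hand can surface here. This stands: the question is ambiguous, not blind. A reader might infer that it mixes existing disability with an injection effect, but that is only one possible reading of its wording.
- **Numbness.** Only one of the three diagnoses has it as an entry feature, and there it is intermittent with nocturnal symptoms. A patient free of numbness in clinic, or numb afterwards in a different area, could properly answer yes. This also stands, and it means that the missed fraction is probably below 1. It does not help the patient whose existing numbness deepens.
- **Case mix.** The carpal tunnel share may be small. In the patient questionnaire (section 1.3), 1 of the 10 patients with a previous injection had it for carpal tunnel syndrome and 9 for trigger finger. That is a small convenience sample, but it is the only indication given and it does not support assuming a large share.
- **Other routes.** Section 5.2 asks for all adverse events to be recorded. No active question about numbness is described there, so this is a weak safeguard.
- **Forms not seen.** The participation record and the full assessment record are not in the supplied text, so a baseline item on them cannot be excluded. It would not change the question wording printed in the protocol.
- **Consequence.** The outcome is secondary and untested, so no formal comparison is weakened. This stands and limits the importance of the point.

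**Conclusion.** The point holds in a limited form. Worsening of existing numbness is not asked about, although section 1.2 names it as a possible effect of local anaesthetic and carpal tunnel patients can have such numbness at entry. The function question lacks a reference point, so its answers do not clearly measure the worsening that section 7.1 reports. The descriptive numbness and hand-function results may under-count an effect expected mainly in the local anaesthetic arm, and they are hard to interpret in patients impaired at entry.

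A reader might infer that objective iii cannot be answered in these patients. The documents do not support that. The objective names analgesia and use of the hand, not numbness; the analgesia question does not depend on the state of the hand at entry; and the function question can still capture worsening. The numbness question matters because sections 3.1 and 7.1 draw the outcome from all three answers.

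The size is unknown without the case mix and the true rates. The primary non-inferiority conclusion and the sample size are unaffected. This is a free improvement, not a flaw that threatens the trial.

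**What to change.** Reword two questions on the patient assessment record and in sections 3 and 3.1:

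- Numbness: *Did you have any new numbness in your hand, or worsening of numbness you already had, as a result of the injection?* Answers: new / worse / no.
- Function: *Compared with just before the injection, did your hand function get worse as a result of the injection?* Keep the free-text line.

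Then define the hand-function and numbness outcomes in section 7.1 (objective iii) by these answers. The function wording carries its own reference point, so a separate baseline item is not strictly needed; it relies on recall over 3 hours.

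The cost is a revised form and the amendment review described in section 9.1. It needs no extra patients, visits or analysis. If the present form is already in use when the change is made, report answers to the two wordings separately.

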7.2 THE NUMBER OF PARTICIPANTS

Minimally clinical important difference of 20mm will be used as the clinically admissible margin of non-inferiority. From previous studies, it is assumed to use a standard deviation of 25mm and with a 95% power calculations have determined a required sample size of 41 per study arm, when including a 20% fall out rate a total sample size of 100 patients will be required²².

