7.3 THE LEVEL OF STATISTICAL SIGNIFICANCE

. All statistical testing was done at the two-sided 5% significance level, and 95% CIs with Stata 14.2.

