7.4 RANDOMISATION

Patients will be randomised using the simple randomisation service provided by Sealed Envelope Ltd (<https://www.sealedenvelope.com>). This is an online service that provides random permuted block randomisation, ensuring participants are balanced between the control and treatment group.

7.5 CRITERIA FOR THE TERMINATION OF THE TRIAL.

Once 100 patients have been recruited and randomised to the trial.

7.6 PROCEDURE FOR ACCOUNTING FOR MISSING, UNUSED, AND SPURIOUS DATA.

A 20% fall out rate has been considered. Participants who have not returned their patient assessment records will not be included in the analysis. Results from partially completed forms will be included for analysis.

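### The 82 evaluable patients, 20% fall-out and 100 randomised do not agree: 20% loss from 100 leaves 80, and power is slightly below the stated 95%

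*Combined protocol and SAP*

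**What the plan says.** Section 7.2 sets the planning inputs. The margin is given as "Minimally clinical important difference of 20mm will be used as the clinically admissible margin of non-inferiority". For variability, "it is assumed to use a standard deviation of 25mm". The result is "a required sample size of 41 per study arm" at 95% power, that is 82 in total. The same sentence continues: "when including a 20% fall out rate a total sample size of 100 patients will be required".

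Section 3.1 shows how 82 became 100: the target is a figure "which includes 82 patients to achieve 95% power, plus 20% to account for potential dropouts".

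Section 7.6 repeats the 20% fall-out rate and leaves out of the analysis anyone who does not return the assessment record. Section 4.1 fixes recruitment at 100 randomised and treated, and section 7.5 ends the trial when 100 have been recruited and randomised. On significance, section 7.3 says "All statistical testing was done at the two-sided 5% significance level". No section states the true difference assumed in the sample size calculation.

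**The concern.** A fall-out rate is normally a proportion of those who enter the trial. Read that way, 20% of 100 is 20 patients, and 80 remain. The plan says that it needs 82. The wording of section 3.1 suggests the cause: the 20% was taken of the 82 and added on, when it should have been divided out.

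What is at stake is the accuracy of the sample size justification. If losses run exactly as the plan expects, the trial ends with fewer evaluable patients than the number to which it ties its 95% power. Anyone who checks the paragraph will find this in one line of arithmetic, so it is worth correcting even though little power is involved.

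**Working it through.** **Inputs**
- Margin 20 mm, SD 25 mm, power 95%, fall-out 20%: section 7.2.
- Alpha: two-sided 5% (section 7.3), taken as one-sided 2.5% for the non-inferiority bound.
- Equal allocation: 41 in each arm (section 7.2), with "random permuted block randomisation, ensuring participants are balanced between the control and treatment group" (section 7.4).
- True difference 0 mm: an assumption, not stated in the documents.

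**Step 1. Reproduce the plan's 41 per arm (normal approximation).**

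n per arm = 2 × (SD/margin)² × (z₀.₉₇₅ + z₀.₉₅)² = 2 × (25/20)² × (1.960 + 1.645)² = 40.6, rounded up to 41, so 82 in total.

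This matches the plan exactly. A one-sided 5% level would give 33.8, rounded up to 34 per arm, which does not match. The inputs above are therefore very probably the ones used.

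**Step 2. From 82 to 100.**
- Added on: 82 × 1.2 = 98.4. By arm, 41 × 1.2 = 49.2, rounded up to 50, and 2 × 50 = 100. This is consistent with the stated total.
- Divided out: 82/0.8 = 102.5, rounded up to 103. By arm, 41/0.8 = 51.25, rounded up to 52, or 104 in total. This is not consistent with it.

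**Step 3. What 100 randomised supports.**
- At 20% loss: 100 × 0.8 = 80 evaluable, 40 per arm.
- Loss that still leaves 82: 1 − 82/100 = 18%.

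**Step 4. Power at 40 and 41 per arm.**

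Normal approximation: power = Φ(margin/(SD × √(2/n)) − 1.960).
- n = 40: 20/(25 × √(2/40)) = 3.578; 3.578 − 1.960 = 1.618; power 94.7%.
- n = 41: 20/(25 × √(2/41)) = 3.622; 3.622 − 1.960 = 1.662; power 95.2%.

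The t-test figures use the noncentral t distribution with 2n − 2 degrees of freedom and the same noncentrality (3.578 or 3.622).

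| Evaluable per arm | Normal approximation | t-test |
|---|---|---|
| 40 | 94.7% | 94.2% |
| 41 | 95.2% | 94.7% |

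Going from 41 to 40 per arm costs about 0.5 percentage points by either method. By the t-test, 40 per arm is 0.8 points below 95%. Of that, 0.5 comes from the dropout slip and 0.3 from the choice of formula.

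**The case against.** Five things can be said for the plan.

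1. **Section 3.1 taken alone is not contradictory.** Read literally, 82 plus a fifth of 82 is 98.4, and 100 covers it. The conflict appears only when the 20% is a share of those randomised. That is the natural meaning of the fall-out rate in sections 7.2 and 7.6, so the three figures still need reconciling. But this is a loosely described allowance and leaves the 41 per arm intact.

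2. **The gap is smaller than the uncertainty in the inputs.** At 40 per arm, an SD of 24.8 mm (normal) or 24.5 mm (t-test), in place of the assumed 25 mm, restores 95%. The 20% is itself a planning guess, and 18% would leave exactly 82. This stands, and it is why the point is minor.

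3. **The normal approximation is routine for planning.** A reader might infer that 41 per arm is itself wrong, because the t-test in section 7.1 reaches 95% only at 42 per arm (95.2%). The documents do not support calling that an error. They name no planning formula, and section 7.1 makes the t-test conditional on the distribution of the scores.

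4. **Missing 1-hour scores.** A reader might infer a further loss from forms returned without the primary score. The documents give no rate for this. Section 7.6 does not limit the 20% to unreturned forms, so counting such losses again could double-count. Section 3 also plans a call after the 24-hour score to check that the form is complete.

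5. **Sidedness is not stated with the sample size.** Section 1.1 describes non-inferiority as a one-sided test. If that meant one-sided 5%, 40 per arm would give about 97% power. Since 41 per arm reproduces only at one-sided 2.5%, the figures here use that level, but the point shows why the alpha should be written into section 7.2.

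**Conclusion.** The inconsistency is real. Under the plan's own 20% loss, 100 randomised yields 80 evaluable patients, not 82, and power is 94.7% (normal approximation) or 94.2% (t-test), against a stated 95%. These values rest on SD 25 mm, margin 20 mm, one-sided 2.5%, equal arms and a true difference of zero. The last of these is assumed because the documents do not give it.

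A reader might infer that the trial is underpowered or that the promised power is lost. The figures do not support that. The shortfall is two patients, the slip costs about half a percentage point, and 94.7% rounds to the stated value. This is a minor correction to the justification. It does not affect conduct, the analysis or the interpretation of the result.

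**What to change.** Keep 100 and bring sections 3.1 and 7.2 into line with wording such as: *100 randomised allows for 18% loss while keeping 82 evaluable patients (41 per arm); at 20% loss, 80 evaluable (40 per arm) gives about 94-95% power, for SD 25 mm, a 20 mm margin, one-sided 2.5% and an assumed true difference of zero.* The authors should confirm that this alpha and this true difference are what they used. The fall-out figure in section 7.6 should then be read in the same way.

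The cost is about two sentences and no extra patients. The quoted power becomes slightly less favourable. Keeping both the 20% loss and the 82 evaluable would instead mean 103 randomised, or 104 for equal arms. For half a point of power, that is not needed.
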